8.2.2 ADA and safety

Adverse events and SAEs during the study (separately for on-treatment and on-study periods) will be summarized by ADA status (treatment-emergent ADA positive, ADA negative), if enough data are available. The on-treatment and on-study periods are as defined in Section 3.4.1. AEs and SAEs will also be evaluated by causality as assessed by the Investigator. The potential impact of ADA on hypersensitivity will also be assessed if enough data are available.

8.2.3 ADA and eosinophil levels

Eosinophil levels will be summarized by visit for the following ADA response categories of participants: treatment-emergent ADA positive, ADA negative, ADA persistently positive, and ADA positive with titre > median of maximum titre, if enough data are available. A line plot of eosinophil levels by visit and ADA status will also be presented.

8.2.4 ADA and PK

Benralizumab serum concentrations will be summarized by visit and ADA status (treatment emergent ADA positive, ADA negative, ADA persistently positive, ADA positive with titre > median of maximum titre) for participants in the PK analysis set, if enough data are available.

8.3 Partial dates for adverse events and prior/concomitant medications

Dates missing the day, or both the day and month of the year will adhere to the following conventions to classify TEAEs and to classify prior/concomitant medications:

Adverse events

- The missing start day will be set to:
 - First day of the month of occurrence, if the start YYYY-MM is after the YYYY-MM of first study treatment
 - The day of the first study treatment, if the start YYYY-MM is the same as YYYY-MM of the first study treatment
 - The date of informed consent, if the onset YYYY-MM is before the YYYY-MM of the first study treatment.
- The missing end day will be set to:
 - The last day of the month of the occurrence, if the end YYYY-MM is after the YYYY-MM of the first study treatment.
 - Death date if the participant died in the same month.
 - The day of last study treatment if the YYYY-MM of occurrence is the same as the last study treatment.
- If the start date is missing both the day and month, the start date will be set to:
 - January 1 of the year of occurrence.
 - The date of the first study treatment, if the start year is the same as the year of the first study treatment
- If the end date is missing both the day and month, the date will be set to:
 - December 31 of the year of occurrence.
 - Date of death if the participant died in the same year
 - Last study treatment date if the year of occurrence is the same as the last study treatment date.
- If the start date is null, the date will be set to:
 - The date of first study treatment.
 - January 1 of the same year as the end date, if the end date suggests that the start date could be prior to the date of first study treatment.
- If the end date is null and not recorded as ongoing, the date will be set to:
 - The date of the first study treatment, if the start date is prior to the date of first study treatment.
 - The date of last visit, if the start date is on or after the date of first study treatment.

- If the end date is null and recorded as ongoing, the end date will not be imputed.

Prior/concomitant medication

- The missing day of start date of a therapy will be set to the first day of the month that the event occurred.
- The missing day of end date of a therapy will be set to the last day of the month of the occurrence.
- If the start date of a therapy is missing both the day and month, the onset date will be set to January 1 of the year of onset.
- If the end date of a therapy is missing both the day and month, the date will be set to December 31 of the year of occurrence.
- If the start date of a therapy is null and the end date is not a complete date, then the start date will be set to the earlier of the imputed partial end date and the date of the first study visit.
- If the start date of a therapy is null and the end date is a complete date
 - and the end date is after the date of the first study visit then the start date will be set to the date of the first study visit.
 - otherwise, the start date will be set to the end date of the therapy.
- If the end date of a therapy is null and the start date is not a complete date, then the end date will be set to the study end date.
- If the end date of a therapy is null and the start date is a complete date
 - and the start date is prior to the study end date, then the end date will be set to the study end date.
 - otherwise, the end date will be set to the start date of the therapy.

SIGNATURE PAGE

This is a representation of an electronic record that was signed electronically and this page is the manifestation of the electronic signature

Document Name: d3256c00001-sap-ed-2		
Document Title:	Statistical Analysis Plan Edition 2	
Document ID:	CCI [REDACTED]	
Version Label:	2.0 CURRENT LATEST APPROVED	
Server Date (dd-MMM-yyyy HH:mm 'UTC'Z)	Signed by	Meaning of Signature
19-May-2022 11:52 UTC	PPD [REDACTED] IQVIA	Author Approval
18-May-2022 17:31 UTC	PPD [REDACTED]	Content Approval

Notes: (1) CCI [REDACTED]

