3.1.5 Intercurrent Events

Intercurrent events are withdrawal from the study at any time or requiring rescue therapy from Day 29 onwards. However, participants who started on placebo and switched to benralizumab in the extension phase are additionally permitted rescue therapy for 28 days from starting benralizumab, and thus additionally any rescue therapy use from Day 141 (ie 29 days after first dose of benralizumab) onwards will be considered as intercurrent event for these participants.

Withdrawal from the study will be considered from the day after withdrawal onwards, thus data on the day of withdrawal will be used as recorded. Rescue therapy from Day 29 (of first dose, and additionally for placebo-benralizumab participants from first benralizumab dose) onwards will be considered for intercurrent event imputation from the day of taking rescue medication onwards.

For responder or binary analyses, participants with intercurrent events will be considered as non-responders from the time these events occur. Participants with missing data for binary endpoints will also be considered non-responders at affected post baseline visits. Intercurrent events will be considered for analyses and descriptive summaries.

For change from baseline analyses or number and percentage of score category summaries, participants with intercurrent events will be considered as having missing scores from the time these events occur. Intercurrent events will be considered for analyses and descriptive summaries.

For summaries of number and percentage of individual questionnaire scores, all data will be presented as recorded, without imputation for intercurrent events.

The categorisation and imputations of responder status and reasons for non-response are provided in following table.

Table 3 Response Category Imputations

Response Category	Imputation Rule
Responder	Keep data as recorded, unless after taking rescue medication
Non responder	
Recorded as non-responder	Keep data as recorded, even if after taking rescue medication

Table 3 Response Category Imputations

Response Category	Imputation Rule
Missing	For missing questionnaire/visit, where participant remains in study and could be Responder or Recorded Non-responder or Rescue medication and remain in study
Rescue medication and remain in study	Impute if recorded as Responder and participant ongoing in study. Impute from day of rescue medication onwards, but only for assessments where participant is a Recorded Responder

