3.4.1 Adverse Events

AEs (including SAEs) experienced by the participants will be collected throughout the entire study and will be coded using the latest version of the Medical Dictionary for Regulatory Activities (MedDRA) that will have been released for execution at AstraZeneca/designee per the Data Management Plan.

AEs for the 16-week placebo-controlled analysis reporting will include all AEs with start date prior to entering the extension period.

AEs for the Week 52 end of study reporting over the entire study duration will include all AEs as defined below. AEs reported for the extension period alone are those with start date on or after the date of first dose of treatment during the extension period.

As per CSP Section 9.4.3, the following events are considered treatment emergent:

- AEs with an onset date on or after the first dose of IP;
- Worsening of pre-existing events on or after first dose of IP.

For the analysis, an AE will be defined as Treatment Emergent AE (TEAE) if it has an onset date on or after the first dose of IP. Applying this definition, also the worsening of pre-existing events on or after the first dose of IP will be included in the analysis as Investigators are instructed to record these as new events.

AE data will be categorized according to their onset date into the following study periods:

- AEs in the pre-treatment period are defined as those with an onset prior to the day of first dose of IP.
- AEs in the on-treatment period for 16-week placebo-controlled period are defined as those with onset date between day of first dose of IP and the day prior to first dose in extension period; or the last dose in placebo-controlled period + 30 days for those who do not enter the extension period.
- AEs in the on-treatment period for extension period only are defined as those with onset date between day of first dose of IP in the extension and the last dose + 30 days.
- AEs in the on-study period for Week 52 end of study reporting are defined as those with onset on or after the day of first dose of IP.

If an AE has a missing onset date then unless the stop date of the AE indicates otherwise, this will be considered an on-treatment AE. Similarly, if an AE has a partial onset date, then unless

the partial onset date or the stop date indicates otherwise, this will be considered an on-treatment AE.

AEs that have missing causality (after data querying) will be assumed to be related to study drug.

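### SAP 8.3 has no partial-date rule for the first extension dose, so an AE with missing onset day in that month is almost always counted in the 16-week placebo-controlled period

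*SAP*

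**What the plan says.** Section 3.4 sends partial AE dates to Appendix 8.3, which opens: "Dates missing the day, or both the day and month of the year will adhere to the following conventions to classify TEAEs". The same sentence extends the conventions to prior and concomitant medication.

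For AE starts, 8.3 uses only first study treatment and informed consent as anchors:

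- Day missing, same month as first treatment: the day of first treatment.
- Day missing, later month: "First day of the month of occurrence, if the start YYYY-MM is after the YYYY-MM of first study treatment".
- Day and month missing: 1 January, or "The date of the first study treatment, if the start year is the same as the year of the first study treatment".

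Section 3.4.1 assigns events to periods by onset. The 16-week on-treatment period ends the day before the first extension dose. Extension events are "those with onset date between day of first dose of IP in the extension and the last dose + 30 days". Its fallback for a partial onset says only that the event is on-treatment, and both periods are on-treatment periods.

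For medications, 8.3 says: "The missing day of start date of a therapy will be set to the first day of the month that the event occurred". Section 3.1.5 makes rescue an intercurrent event by time: "Rescue therapy from Day 29 (of first dose, and additionally for placebo-benralizumab participants from first benralizumab dose) onwards". It gives Day 141 as the later threshold for placebo participants who switch. Section 3.1.4 says no medication data are imputed beyond what is needed for prior/concomitant assignment.

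**The concern.** 8.3 is cautious at the first treatment change: an undated event in the month of first dose is treated as on treatment. At the second change, Week 16, it has no counterpart. That is where placebo participants start benralizumab and where the main safety period ends. Section 4.2.8.1 names the 16-week on-treatment period as the primary period for safety summaries, so a rule that routinely pulls post-switch events back into it blurs the only placebo-controlled safety comparison. In the placebo column, events that began on benralizumab would be read as placebo events. In the benralizumab column, extension events would be added to 16-week events. In the exposure-adjusted rates the numerator moves while the time at risk does not.

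The secondary question is rescue medication. Rescue matters for the primary endpoint only from Day 29. If the first-of-month start rule were used for that decision, a partly dated record could land before the threshold.

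**Working it through.** **Study days.** Section 3.1.3 defines study day as date minus randomization date plus 1. Week 4 is 28 + 1 = Day 29 and Week 16 is 112 + 1 = Day 113. Then 113 + 28 = 141 reproduces the threshold in 3.1.5. I assume first dose on the randomization date and the extension dose on Day 113. Week 16 is then always in a later calendar month than the first dose, so the first-of-month rule always applies in the switch month.

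**AE example.** Randomized 15 February 2021; first extension dose 112 days later, 7 June 2021. An AE starting 20 June (Day 126) with day missing becomes 1 June (Day 107). It is counted in the 16-week period, although 24 of the 30 June days are on or after the switch.

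**General size.** Take a 30-day month, with the dose on day k (k = 1 to 30 equally likely) and true onset equally likely on each day.

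- Onsets truly on or after the dose: sum of (31 − k) over k = 1 to 30, divided by 900 = 465/900 = 51.7%.
- Records placed before the dose: all except k = 1, 29/30 = 96.7%.
- Records in the wrong period: sum of (31 − k) over k = 2 to 30, divided by 900 = 435/900 = 48.3%.
- Share of true post-switch onsets misplaced: 435/465 = 93.5%.

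Enumeration over 1,461 consecutive randomization dates with real month lengths gives 51.6%, 96.7%, 48.4% and 93.6%. A later end date does not correct this, because the current rule never moves the onset to the dose date.

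**Same check on the proposed rule.** Suppose the recorded end date is D days after onset. The new rule is wrong only when onset precedes the dose and the end does not, so the error share is the sum of min(D, k − 1) over k = 1 to 30, divided by 900.

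| Event length | Wrong period, proposed rule | Wrong period, current rule |
|---|---|---|
| D = 3 | 84/900 = 9% | 48% |
| D = 7 | 182/900 = 20% | 48% |
| D = 14 | 315/900 = 35% | 48% |
| D ≥ 29, or no end date | 435/900 = 48% | 48% |

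**Rescue.** For the same participant Day 29 is 15 March 2021. Rescue taken on 20 March with day missing gets a start of 1 March, which is Day 15. Judged by imputed start, it precedes the threshold. Under 8.3 a missing end day becomes 31 March, so judged as a period of use it passes the threshold. The SAP does not say which test applies.

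**The case against.** **The rule change swaps one error for another.** About half of undated switch-month events truly began before the switch, and sending all of them to the extension would misplace that half. This stands only where no end date is known or the event is long. With a known end date the proposed rule does better, and at worst it equals the current one. Which way to err for ongoing events is then a matter of convention.

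**Nothing is lost.** The Week 52 on-study summaries count every AE from first dose. That is true, but it does not help the 16-week comparison.

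**A reader might infer that the rules favour the drug.** The SAP does not support this. All arms pass Week 16 and all receive benralizumab after it, with 80 planned on each side of the 16-week comparison. Undated extension events are pulled into both columns, and at similar event rates both gain about equally.

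**A reader might also infer that rescued participants will stay responders on the primary endpoint.** The SAP does not establish that either. The scope of 8.3 is prior/concomitant assignment, 3.1.5 speaks of rescue use rather than its start date, and the end-date rules in 8.3 would often carry use past Day 29. A missed flag could equally help a placebo participant. What stands is that no rule is stated.

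**Conclusion.** The AE gap is real and follows from 3.4.1 and 8.3 read together. A day-missing onset in the month of the first extension dose goes to the 16-week period in about 97% of cases, and about 48% of such records are put in the wrong period. These percentages assume evenly spread onset and dose dates, and they apply only to day-missing records in that one month. The SAP cannot give the number of such records, so the effect on any AE table cannot be sized and may be small. The net direction between arms is not established.

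The rescue point is conditional: an error arises only if timing is judged by an imputed start date. If it did, one participant would move an 80-person arm by 1/80 = 1.25 percentage points. That is a ceiling, because Table 3 changes the result only for a recorded responder, and only if no other dated rescue from Day 29 already applies.

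This is a minor clarification, worth making because it is cheap.

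**What to change.** **AE dates (main change).** Add to 8.3: if the start month and year of an AE equal those of the first extension dose, onset is set to the date of that dose, unless the end date or other recorded information places it earlier. Apply it identically in all arms. Every participant who enters the extension has this date, so it can be programmed without unblinding.

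Keep this at month level. A matching rule for year-only dates is not advisable: when both doses fall in one calendar year, it would move many events that truly began before the switch.

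**Rescue flag (secondary).** State that, for the intercurrent-event flag only, a partly dated rescue record counts as use on or after the threshold already in 3.1.5 (Day 29 or Day 141) unless its end date rules this out. The first-of-month start rule then cannot place it before the threshold.

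**Cost.** Two sentences and small program changes. Some long or ongoing AEs that truly began just before the switch will be counted in the extension. Likewise, some rescue use that truly preceded the threshold will be counted after it.
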